6.1.7. Reproductive Hormone Stopping Criteria

If a subject experiences significant changes from baseline in reproductive hormone(s), the Investigator should determine whether such changes represent clinically significant reproductive abnormalities, potential risks to the subject, whether to discontinue study drug, and appropriate safety follow-up. These changes include but are not limited to significant changes in LH, FSH, sex hormone-binding globulin (SHBG), estradiol, prolactin, progesterone, or menstrual cyclicity.

6.1.8. Platelet Stopping Criteria

- Platelet counts $<75,000/\mu\text{L}$ (Grade 3) should be confirmed with repeat laboratory testing within 72 hours of receipt of the initial test results.
- Platelet counts $<75,000/\mu\text{L}$ should be monitored every 48 to 72 hours; if they decrease below $50,000 \text{ mm}^3$, fail to normalize after 7 days, or clinical complications of thrombocytopenia develop, drug should be discontinued immediately, and the subject withdrawn from the study.
- Platelet counts $<50,000/\mu\text{L}$ should retest as soon as possible and discontinue drug immediately with withdrawal of the subject if testing is confirmatory.

6.1.9. Study Stopping Criteria

If any of the following criteria are met, the study will be stopped.

1. If 3 or more subjects on active drug experience a drug-related AESI
2. If 1 or more subjects on active drug experience a drug-related TEAE that is serious (TESAE) and results in death (Grade 5)
3. Any other safety trend or finding that creates an unacceptable risk-benefit profile for subjects participating in the study

Intensity should be evaluated per definitions in [Section 7.2.3.1](#). Seriousness criteria are provided in [Section 7.2.2](#). An unblinded Medical Monitor separate from the study team will monitor if study stopping criteria are met.

6.1.10. Clinically Significant Adverse Events

Clinically significant AEs include but are not limited to SAEs, AEs leading to study drug discontinuation/study withdrawal (eg, based on stopping criteria in [Section 6.1](#)), DLTs ([Section 6.1.1](#)), and AESIs ([Section 7.2.8](#)).

The Investigator should consider study drug discontinuation and appropriate safety follow-up for a subject who experiences a potentially clinically significant AE. When feasible, the Investigator should contact the Medical Monitor to discuss the subject's clinical condition before discontinuing study drug.

6.2. Subject Withdrawal from the Study

Subjects are free to withdraw from the study at any time upon request. If the subject withdraws consent for disclosure of future information, the Sponsor may retain and continue to use any data collected before the withdrawal of consent. The subject may request destruction of any samples taken and not tested, and the Investigator must document this in the site study records.

Subjects will be withdrawn from the study by the Investigator and/or Sponsor for either of the following:

- Pregnancy
- If any clinical AE, laboratory abnormality, or other medical condition or situation occurs such that continued participation in the study would not be in the best interest of the subject

A subject may also be withdrawn from the study by the Investigator and/or Sponsor at any time for other safety, behavioral, compliance, or administrative reasons such as the following:

- Significant protocol deviation or noncompliance with study procedures/restrictions
- If the subject no longer meets eligibility criteria
- Study termination by the Sponsor

If possible, an Early Termination Visit (see Schedule of Activities in [Section 12.2](#)) should be conducted before subject withdrawal. The Investigator must document the date and primary reason for the withdrawal on the appropriate eCRF. Subjects who withdraw prematurely may be replaced at the discretion of the Sponsor to ensure adequate numbers of evaluable subjects.

6.3. Lost to Follow-up

A subject will be considered lost to follow-up if the subject fails to attend scheduled visits and study personnel are unable to reach the subject.

The following actions must be taken if a subject fails to attend a required study visit:

- The site must attempt to contact the subject and reschedule the missed visit as soon as possible, counsel the subject on the importance of maintaining the assigned visit schedule and ascertain whether the subject wishes to and/or should continue in the study.
- Before a subject is deemed lost to follow-up, the Investigator or designee must make every effort to regain contact with the subject, including, where possible, making 3 telephone calls to the subject and, if necessary, sending a certified letter to the subject's last known mailing address (or local equivalent methods). Attempts to contact the subject should be documented in the subject's medical record.
- If the subject continues to be unreachable, the subject will be considered to have withdrawn from the study with a primary reason of lost to follow-up.

7. STUDY ASSESSMENTS AND PROCEDURES

The timing of study assessments and procedures is provided in the Schedule of Activities in [Section 12.2](#).

7.1. Safety Assessments

Safety assessments will include monitoring and recording all AEs (including SAEs, AEs leading to discontinuation/withdrawal, DLTs, and AESIs), physical examination, vital signs assessment, ECGs, and clinical laboratories, including serum cortisol and monitoring for suicide risk using the C-SSRS. AE procedures are described in [Section 7.2](#).

7.1.1. Physical Examination

A full physical examination should include assessments of the cardiovascular, respiratory, GI, neurological, and musculoskeletal systems; head, eyes, ears, neck, and throat (HEENT); thyroid; skin; and extremities. The full physical examination may exclude rectal, genitourinary, and breast exams.

An abbreviated physical examination should include the following components: cardiovascular, respiratory, abdomen, musculoskeletal systems, HEENT and skin.

Investigators should pay special attention to clinical signs related to previous serious illnesses.

7.1.2. Vital Signs

Vital signs consist of systolic and diastolic blood pressure, pulse rate, respiration rate, and body temperature. The subject should rest for at least 5 minutes before vital signs measurement without speaking or using a cellphone. The subject should be sitting in an upright position with feet flat on the floor and the measurement arm supported at heart level. Blood pressure should be taken in the same arm at each visit, if possible. Vital signs will be measured as specified in the Schedule of Activities ([Section 12.2](#)) and as clinically indicated.

7.1.3. Body Weight and Height

Total body weight (actual body weight) will be measured as specified in the Schedule of Activities ([Section 12.2](#)) using a calibrated balance. Height will be recorded at the Screening Visit only. BMI will be calculated using these measurements.

7.1.4. Electrocardiogram

A 12-lead ECG will be obtained using an ECG machine that automatically calculates the heart rate, QRS, QT, and QTc intervals, preferably using QTcF. Any ECG measurement assessed by the Investigator as a clinically significant abnormality should be recorded in the AE section of the eCRF and monitored until resolution.

Refer to [Section 6.1.3](#) for QT individual treatment-stopping criteria and any additional ECGs that may be necessary.

7.1.5. Clinical Laboratories

Clinical laboratory assessments include hematology, clinical chemistry, including cortisol, HbA1c, coagulation, lipid panel, thyroid panel, urinalysis, and a hormone panel. eGFR for screening will be calculated from blood creatinine measured as part of Screening clinical chemistry. A complete list of study-required clinical laboratory tests is provided in [Section 12.4](#).

Samples for clinical laboratories will be collected consistently at the beginning of each visit at approximately 8 A.M. See the Schedule of Activities ([Section 12.2](#)).

All study-required clinical laboratory tests must be conducted in accordance with the laboratory manual and will be performed by a central laboratory.

The Investigator must review the laboratory report, document the review, and record any clinically significant laboratory findings that occur during the study in the AE section of the eCRF. Laboratory reports must be filed with the source documents. Clinically significant laboratory findings are those that are not associated with the underlying disease, unless judged by the Investigator to be more severe than expected for the subject's condition.

All laboratory tests with values considered clinically significantly during the Treatment Period or within 30 days after the last dose of study drug should be reported as AEs and repeated at least weekly until the values return to normal or baseline or are no longer considered clinically significant by the Investigator or Medical Monitor. If such values do not return to normal/baseline within a period of time judged reasonable by the Investigator, the etiology should be identified, and the Sponsor notified.

7.1.6. Psychiatric Evaluations

7.1.6.1. Columbia-Suicide Severity Rating Scale (C-SSRS)

The C-SSRS will be used during the study to monitor suicidal ideation and behavior. The C-SSRS is an FDA-endorsed questionnaire administered by trained study personnel to screen for suicidality risk and ideation in patients participating in trials of CNS-active compounds. The Baseline/Screening Version of the C-SSRS, which assesses both lifetime history and history from the last 12 months, will be used at screening to determine subject eligibility. The Since Last Visit Version of the C-SSRS will be used at all subsequent visits specified.

Refer to [Section 6.1.4](#) for suicidality individual treatment-stopping criteria.

7.2. Adverse Events and Serious Adverse Events

7.2.1. Definition of Adverse Event

An AE is any untoward medical occurrence in a subject participating in a clinical trial. Examples of AEs include but are not limited to:

- Clinically significant abnormal test results
- Clinically significant symptoms and signs
- Changes in physical examination findings
- Hypersensitivity
- Progression/worsening of underlying disease

A TEAE is defined as an AE that occurs during or after administration of the first dose of study drug until 30 days after the final dose of study drug (Follow-up Visit). For AEs that occur on the date of the first dose of study drug, the time of onset (before or after intake of study drug) must be specified.

An abnormal test result should be reported as an AE if any of the following criteria are met:

- It is associated with accompanying symptoms
- It requires additional diagnostic testing or medical/surgical intervention
- It leads to a change in study drug dosing or study drug discontinuation, significant additional concomitant drug treatment, or other therapy
- It is considered to be an AE by the Investigator or Sponsor

Merely repeating an abnormal test, in the absence of any of the above conditions, does not constitute an AE. Any abnormal test result that is determined to be an error does not require reporting as an AE.

Examples of events that do not meet the definition of an AE include but are not limited to:

- Clinically significant abnormal test result or other abnormal safety assessment associated with the underlying disease, unless it is more severe than expected for the subject's condition
- The underlying disease and its signs and symptoms, unless they are more severe than expected for the subject's condition
- Medical and surgical procedures; the condition that leads to the procedure is the AE if it meets the definition of an AE. For example, an acute appendicitis that begins during the AE reporting period should be reported as the AE, and the resulting appendectomy should be recorded as treatment for the AE
- Anticipated day-to-day fluctuations of pre-existing disease(s) or condition(s) present or detected at the start of the study that do not worsen

7.2.2. Definition of Serious Adverse Event

An SAE or serious adverse drug reaction is any untoward medical occurrence at any dose that meets any of the following criteria:

- Results in death
- Is life threatening (immediate risk of death)
- Requires inpatient hospitalization or prolongation of existing hospitalization
- Results in persistent or significant disability/incapacity
- Is a congenital anomaly/birth defect
- Is an important medical event

Medical and scientific judgment should be exercised in determining whether an event is an important medical event. An important medical event may not be immediately life-threatening and/or result in death or hospitalization. However, if it is determined that the event may jeopardize the subject and may require intervention to prevent one of the other outcomes listed in the definition above, the important medical event should be reported as serious.

Examples of such events include allergic bronchospasm that requires intensive treatment in an emergency room or at home, blood dyscrasias or convulsions that do not result in hospitalization, or the development of drug dependency or drug abuse. If either the Sponsor or the Investigator believes that an event is serious, the event must be considered serious and evaluated by the Sponsor for expedited reporting.

Hospitalization does not include rehabilitation, hospice, or skilled nursing facilities; respite care; nursing homes; or same-day surgeries (as outpatient/same day/ambulatory procedures).

Hospitalization or prolongation of hospitalization in the absence of a precipitating clinical AE is not in itself an SAE. Examples include the following:

- Admission for treatment of a pre-existing condition not associated with the development of a new AE or with a worsening of the pre-existing condition (eg, for workup of persistent pre-treatment lab abnormality)
- Social admission (eg, subject has no place to sleep)
- Administrative admission (eg, for yearly physical exam)
- Protocol-specified admission during a clinical study (eg, for a procedure required by the study protocol)
- Optional admission not associated with a precipitating clinical AE (eg, for elective cosmetic surgery)
- Pre-planned treatments or surgical procedures should be noted in the baseline documentation for the entire protocol and/or for the individual subject.

7.2.3. Classification of an Adverse Event

The Investigator must record all AEs in the eCRF with information about:

- Duration (start and end dates)
- Severity ([Section 7.2.3.1](#))
- Relationship to study drug ([Section 7.2.3.2](#))
- Action(s) taken and, as relevant, the outcome ([Section 7.2.3.3](#) and [Section 7.2.3.4](#))
- Seriousness ([Section 7.2.2](#))

7.2.3.1. Severity

The Investigator will assess the severity of each AE according to the National Cancer Institute CTCAE version 5.0 ([CTCAE 2017](#)), which is summarized in [Table 3](#).

Table 3. Severity of Adverse Events

Grade 1: Mild; asymptomatic or mild symptoms; clinical or diagnostic observations only; intervention not indicated.
Grade 2: Moderate; minimal, local, or noninvasive intervention indicated; limiting age-appropriate instrumental ADL (preparing meals, shopping for groceries or clothes, using the telephone, managing money, etc.).
Grade 3: Severe or medically significant but not immediately life threatening; hospitalization or prolongation of hospitalization indicated; disabling; limiting self-care ADL (bathing, dressing and undressing, feeding self, using the toilet, taking medications, and not bedridden).
Grade 4: Life-threatening consequences; urgent intervention indicated.
Grade 5: Death related to AE.

Abbreviations: ADL, activities of daily living; AE, adverse event.

Note the distinction between the severity and the seriousness of an AE. A severe event is not necessarily a serious event. Severe is a category used for rating the intensity of an event, and both AEs and SAEs can be assessed as severe. For example, a headache may be severe (interferes significantly with subject's usual function) but would not be classified as serious unless it met at least one of the criteria for an SAE listed in [Section 7.2.2](#), such as resulting in hospitalization.

If there is a change in the severity of an ongoing AE, it will be recorded as part of the same event, with the worst grade of severity for the entire event timeframe being recorded.

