3.1.1. Dose Escalation

Subjects randomized to the tildacerfont group will initiate treatment with 4 weeks of 50 mg QD, then proceed to 4 weeks at 100 mg QD and complete the study with 4 weeks at 200 mg QD. All placebo subjects will remain on placebo over the full 12-week treatment period. If signs, symptoms or biochemical evidence of adrenal insufficiency are noted, study drug will be suspended until adrenal function may be fully evaluated for relationship to clinical findings. If adrenal insufficiency is confirmed, study drug will be permanently discontinued and treatment will be managed by the Investigator according to standard medical practice. Complete stopping criteria for adrenal insufficiency are provided in [Section 6.1.6](#).

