6.1.1. Dose-Limiting Toxicity Stopping Criteria

A dose-limiting toxicity (DLT) is defined as a Common Terminology Criteria for Adverse Events (CTCAE) Grade 3 or higher treatment-emergent AE (TEAE) considered at least possibly related to study drug. If a subject experiences a DLT, study drug will be discontinued. DLTs are clinically significant AEs (see [Section 6.1.9](#)).

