9.3.16 Adverse Events

AEs are those AEs with onset date from the signing of the ICF until the end of the follow up period.

Treatment-emergent adverse events (TEAEs) are defined as any AEs, regardless of relationship to study drug, that have an onset or worsening in severity on or after the first dose of study drug until 30 days after the final dose of study drug (Follow-up visit). For AEs that occur on the date of the first dose of study drug, the time of onset (before or after intake of study drug) will be specified and used for comparison.

If a subject discontinues study drug but remains in the study, AEs with onset date after 30 days of last dose of study drug until the end of the follow up period will be considered post-treatment adverse events.

Related TEAEs are those reported by investigators as possibly related, probably related, or definitely related to the study drug.

AESIs are events that do not meet SAE criteria but must be monitored on an ongoing basis as defined in Protocol [Section 7.2.8](#) and identified in the AE eCRF page.

Serious AEs (SAEs) are defined in Protocol [Section 7.2.6](#) and identified in the AE eCRF page.

Dose-limiting toxicities are defined as a Common Terminology Criteria for Adverse Events (CTCAE) Grade 3 or higher TEAE that is also considered at least possibly related to study drug.

Suspected unexpected serious adverse reactions (SUSARs) is an AE that is serious, related to study drug, and is not expected in the targeted disease (PCOS).

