9.3.17.1 Record-Level Actual Treatment and Dose for an Adverse Event

TEAEs are those AEs with onset date from the date of first dose of randomized study drug until the end of the study (Follow-up). The treatment will be the randomized study treatment (tildacerfont or placebo) and the dose level (50 mg QD, 100 mg QD, 200 mg QD) will be the actual tildacerfont dose received on the onset date of the TEAE records.

Post-treatment AEs (within 30 days after study drug discontinuation) will be assigned the last treatment and dose level that the subject was on before study drug discontinuation. Post treatment AEs after 30 days post study drug discontinuation will be assigned to no treatment.

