14 SAFETY ANALYSES

Safety will be assessed by AEs, SAEs, AEs leading to discontinuation/withdrawal, DLTs, AESIs, physical examination, vital signs, ECGs, clinical laboratory tests, and psychiatric evaluations for suicide risk by C-SSRS. All analyses of the safety data will be performed using

the safety analysis set, based on the actual treatment a subject received. All descriptive statistics (described in Section 9.1) will be presented by treatment group (including dose level).

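### An adverse event that worsens after a dose escalation is tabulated at its worst grade under the dose at onset, and the SAP's two TEAE definitions disagree on whether worsening counts

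*Protocol*

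**What the plan says.** **Escalation.** Under Protocol 3.1.1, subjects in the tildacerfont group start with 4 weeks at 50 mg, "then proceed to 4 weeks at 100 mg QD and complete the study with 4 weeks at 200 mg QD".

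**Recording.** When the severity of an ongoing AE changes, Protocol 7.2.3.1 says "it will be recorded as part of the same event, with the worst grade of severity for the entire event timeframe being recorded". The items listed in Protocol 7.2.3 include "Duration (start and end dates"); a date of grade change is not among them.

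**Dose assignment.** SAP 9.3.17.1 says the dose level "will be the actual tildacerfont dose received on the onset date of the TEAE records". SAP 14 says descriptive statistics "will be presented by treatment group (including dose level"), and the protocol synopsis also plans safety summaries by treatment group and dose level.

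**Treatment-emergence.** SAP 9.3.16 covers events "that have an onset or worsening in severity on or after the first dose of study drug". SAP 9.3.17.1 says "TEAEs are those AEs with onset date from the date of first dose of randomized study drug until the end of the study". Protocol 7.2.1 refers to events that occur during or after the first dose and does not mention worsening. Protocol 7.2.4 says AEs between consent and first dose are recorded but are not TEAEs.

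**DLT.** Protocol 6.1.1 defines it as a CTCAE "Grade 3 or higher treatment-emergent AE (TEAE) considered at least possibly related to study drug", and SAP 9.3.16 does the same. An event that is not a TEAE cannot be a DLT.

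**The concern.** Worsening of an ongoing event after a dose increase is one of the signals that a within-subject escalation can show. The plan makes it plausible here: Protocol 1.2.1 and 1.2.2 give a half-life of about 60 hours and steady state after about 2 weeks, so exposure keeps building after each step.

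The recording rule keeps the worst grade, and the dose rule keeps the onset date. Together they pair a late grade with an early dose. The by-dose severity and DLT tables would then credit a lower dose with a grade that was reached at a higher one. SAP 9.3.17.2 provides flags for a medication taken across several dose levels; there is no counterpart for AEs.

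The second issue is one of classification. An event that starts after consent, is ongoing at first dose and then worsens on drug is a TEAE or not according to which SAP section the programmer follows. SAP 4 says the SAP governs where it differs from the protocol, but that cannot settle a conflict inside the SAP.

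**Working it through.** The plan states no figure on this point, so there is nothing to reproduce. The check applies the rules to hypothetical records, with Days 1–28 at 50 mg, Days 29–56 at 100 mg and Days 57–84 at 200 mg.

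**1. Rules applied to example records**

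| Onset day | Day Grade 3 reached | Dose under SAP 9.3.17.1 | Dose when Grade 3 reached | TEAE, SAP 9.3.16 | TEAE, SAP 9.3.17.1 and Protocol 7.2.1/7.2.4 |
|---|---|---|---|---|---|
| 14 | 40 | 50 mg | 100 mg | yes | yes |
| 14 | 70 | 50 mg | 200 mg | yes | yes |
| 40 | 70 | 100 mg | 200 mg | yes | yes |
| 70 | 80 | 200 mg | 200 mg | yes | yes |
| −10 | 70 | none (pre-dose) | 200 mg | yes | no |

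The first three rows are placed under too low a dose. The fourth is placed correctly. The fifth is the only one on which the TEAE definitions disagree. Because the planned dose only rises, any misplacement is downward.

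**2. How long an event must last**

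- 200 to 100 mg: the shortest case is onset on Day 56 and Grade 3 on Day 57, a lag of 57 − 56 = 1 day.
- 200 to 50 mg: the shortest case is onset on Day 28 and Grade 3 on Day 57, a lag of 57 − 28 = 29 days, with the event ongoing throughout.

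**3. Share misplaced, by assumed lag**

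Let L be the lag in days from onset to Grade 3, and let Grade 3 be equally likely on each of the 28 days from Day 57 to Day 84. Onset then falls on day d − L.

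- Assigned to a lower dose if d − L ≤ 56, which holds on min(L, 28) of the 28 days. The share is min(L, 28)/28: for L = 3, 3/28 = 11%; L = 7, 7/28 = 25%; L = 14, 14/28 = 50%; L = 28, 28/28 = 100%.
- Assigned to 50 mg if d − L ≤ 28. The share is 0 for L up to 28, then (L − 28)/28: for L = 29, 1/28 = 3.6%; L = 42, 14/28 = 50%.

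Both the lags and the uniform timing are assumptions; the documents give neither. The shares apply only to events that reach Grade 3 during the 200 mg period after a lower-grade onset on treatment. They are not shares of all AEs.

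**4. The TEAE conflict**

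In the fifth record, SAP 9.3.16 makes the event a TEAE because it worsened on drug, and a DLT if related. SAP 9.3.17.1 looks only at the onset date and excludes it, as do Protocol 7.2.1 and 7.2.4. Applying 9.3.16 also requires a date of worsening, which the record described in Protocol 7.2.3 does not list. Even if the event is counted, 9.3.17.1 gives it no dose, because none was being taken at onset.

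**The case against.** The strongest reply is that little can be lost. A DLT leads to discontinuation of study drug (Protocol 6.1.1). The date and reason go on the eCRF (Protocol 6.1), discontinuations are listed and summarized (Protocol 8.3.5.1), and DLTs and TEAEs leading to discontinuation have their own listings (SAP 14.1). A subject who reaches a DLT at 200 mg is seen to stop drug in the third period. This stands: a reader might infer that the rules conceal a dose-related DLT, and the documents do not support that. The error is one of column assignment in by-dose tables.

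A reader might also infer that an event starting at 50 mg could both be misplaced and drop out of the TEAE set. It cannot, because it is a TEAE under every definition. The two problems affect different events.

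Three further points have force:

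- The recording rule applies to an ongoing AE. An intermittent complaint that resolves and recurs would ordinarily have its own start date, and an uninterrupted event of 29 days or more may be uncommon.
- The eCRF and its completion guidelines are not among the documents and may hold grade-change dates. That the single record keeps its first onset date is an inference from the same-event rule and a single start date.
- Protocol 7.2.1 lists worsening of underlying disease as an AE, so some pre-existing conditions may be entered as new events on drug.

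These points limit how often the problem arises. They do not remove it: even if grade-change dates are held, SAP 9.3.17.1 does not use them, and SAP 9.3.16 and 9.3.17.1 still differ.

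**Conclusion.** The point holds within limits. For an AE that stays ongoing across an escalation and rises in grade, the rules as written place the worst grade, including a DLT, under a lower dose than the one at which it was reached. The likelier error is 200 to 100 mg. Independently, SAP 9.3.16 and 9.3.17.1 disagree on pre-dose AEs that worsen on drug.

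The dose rule affects only the by-dose severity and DLT tables. It leaves the discontinuation rules, the DLT listing and the tildacerfont-versus-placebo counts of AEs starting on drug as they are. The definition conflict affects only the classification of pre-dose AEs, which are listed in any case because SAP 14.1 lists all AEs, including non-TEAEs.

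The number of affected events cannot be estimated: the documents give no AE durations or lags, and SAP 15 reports early discontinuation with a small sample without stating the number enrolled. Confidence is medium because the eCRF was not available.

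**What to change.** **SAP 9.3.17.1.** Replace the onset-only wording with the definition in 9.3.16, onset or worsening on or after first dose, and state that it applies throughout. For severity and DLT tables, assign each event to the dose level on the date that grade was reached, counting each subject once in the overall column. Note in SAP 15 that this departs from Protocol 7.2.1 and 7.2.4.

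**Data.** Before database lock, obtain the date of worsening for AEs that span first dose or an escalation and rose in grade. Query the site only where the eCRF does not already hold the date. For DLTs, the recorded discontinuation date is a useful cross-check.

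**Cost.** A short SAP revision and a few queries. Changing the protocol's recording rule or the eCRF guidelines prospectively would achieve little now that the study has been discontinued early.
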